**NIH Principal Investigator:**

[name], CMTB, NHLBI (E)  
National Heart, Lung & Blood Institute (NHLBI)  
National Institutes of Health (NIH)  
[name]  
[name]  
[name]  
[contact]  
E-mail: [contact]

**Other identifying words:** Red cell survival, cohort label, biotin, sickle cell anemia, sickle cell disease

**Principal Investigator:** [name], CMTB, NHLBI (E)

**Estimated duration of study:** 18 months

Subjects of study:	Number	Sex	Age range
Patients with Sickle Cell Disease (SCD) and controls	21*	either	18 and above

(\*The accrual goal is 21 evaluable subjects; however, to cover screenfails, withdrawal, drop-outs and loss-to-follow ups, an accrual ceiling of 40 subjects is allowed).

Cohorts

- SCD pre-transplantation
- SCD post-transplantation
- HbAS
- HbAA (Healthy volunteers)

Project involves ionizing radiation?	No
Project uses "Durable Power of Attorney"?	No
Offsite project?	Yes
Multi-institutional project?	No

## PROTOCOL SUMMARY

### Synopsis

Title:	Red Cell Half Life Determination in Patients with and without Sickle Cell Disease
Study Description:	
This study will use biotin-labeling of red blood cells (RBCs) to determine the mean potential lifespan (MPL) of RBCs in patients with sickle cell disease (SCD) compared to patients who have successfully undergone curative bone marrow transplantation (BMT, allogeneic or autologous), participants with sickle cell trait, and healthy donors without SCD. Previous studies have corroborated the MPL of healthy donor RBCs to be approximately 115 days while RBCs from patients with SCD have a much more variable but consistently shorter MPL of approximately 32 days. Allogeneic BMT is a curative therapy for the treatment of severe SCD with stable, mixed donor-recipient chimerism after BMT sufficient to reverse the sickle cell phenotype by virtue of improved donor red cell survival compared to the ineffective erythropoiesis of SCD. We predict that the hematologic variables associated with red cell survival among patients with SCD vs. participants with SCT and healthy donors can be used to determine the necessary amount of corrected hemoglobin required to overcome the red cell pathology of SCD. Data generated will be used to determine the utility of performing a population study of RBC lifespan in gene therapy treated patients to ultimately target the percentage of transferred globin gene needed to reverse SCD. The data generated will refine our understanding of the degree of correction necessary to reverse the phenotype of SCD.

Objectives:	
Primary Objective: To determine and compare red blood cell survival in patients with SCD, patients with SCD who have undergone BMT, participants with SCT, and healthy donors, and validate the association of red cell survival with known markers of increased red cell survival.
 
Exploratory Objective: To create a mathematical model incorporating RBC survival and reticulocyte count to determine the necessary amount of normal hemoglobin, and therefore vector copy number or amount of transferred globin, required for gene therapy protocols.

Endpoints:	
Primary Endpoint: Red blood cell survival
 
Secondary Endpoints: Relationship of red blood cell survival to hematologic parameters. Antibody detection to biotin.

Study Population:	Healthy volunteers, participants with known SCT or SCD, and patients with SCD who have successfully undergone curative hematopoietic stem cell transplant. No selection will be based upon gender, race, or age (in those 18 years or greater in age). Participants must be available for frequent blood draws required by and for the duration of this study.
Phase:	Pilot
Description of Sites/Facilities Enrolling Participants:	This is a pilot single site study. Participants will be enrolled at the Clinical Center at the National Institutes of Health.
Description of Study Intervention:	The MPL of RBCs from patients with SCD will be compared to patients who have successfully undergone curative BMT, participants with SCT, and healthy donors without SCD, the latter two who serve as donors for patients with SCD who undergo BMT. RBCs will be isolated

Protocol Number: 20-H-0080

PI: [name]

September 20, 2023 Amendment I

**from participant whole blood. RBCs will be biotinylated ex vivo and reinfused the following day. Biotin can be easily tracked via flow cytometry therefore venous sampling will occur at regular intervals until the percentage of biotinylated RBCs has decreased to the lower limit of detection.**

Study Duration: **Estimated 18 months**

## **STATEMENT OF COMPLIANCE**

The trial will be carried out in accordance with International Conference on Harmonisation Good Clinical Practice (ICH GCP) and the following:

- United States (US) Code of Federal Regulations (CFR) applicable to clinical studies (45 CFR Part 46, 21 CFR Part 50, 21 CFR Part 56, and/or 21 CFR Part 312)

National Institutes of Health (NIH)-funded investigators and clinical trial site staff who are responsible for the conduct, management, or oversight of NIH-funded clinical trials have completed Human Subjects Protection and ICH GCP Training.

The protocol, informed consent form(s), recruitment materials, and all participant materials will be submitted to the Institutional Review Board (IRB) for review and approval. Approval of both the protocol and the consent form must be obtained before any participant is enrolled. Any amendment to the protocol will require review and approval by the IRB before the changes are implemented to the study. In addition, all changes to the consent form will be IRB-approved; a determination will be made regarding whether a new consent needs to be obtained from participants who provided consent, using a previously approved consent form.

## 1.0 Introduction and Background

Sickle cell disease (SCD) is a severe hereditary form of anemia in which a mutated form of the beta globin gene distorts red blood cells and decreases red cell survival. Unstable sickle hemoglobin rapidly polymerizes into gelled, aggregated hemoglobin S (HbS) tetramers at low oxygen levels, leading to increased red cell rigidity, oxidative damage of the red cell membrane, distorted red cell morphology, and a shortened red blood cell (RBC) survival. The altered rheology of erythrocytes and chronic hemolysis leads to the numerous downstream effects including activation of monocytes, leukocytes, platelets, plasma proteins and endothelium. This red cell rigidity and subsequent inflammation is responsible for the devastating clinical manifestations of SCD including chronic anemia, viscosity changes, intravascular sludging, stroke, end organ damage, and ultimately, decreased overall survival (1).

Inherent instability of the HbS polymer leads to oxidative damage of the red cell membrane, with subsequent activation of ion channels leading to a dehydrated and acidotic RBC with increased risk for hemolysis and decreased lifespan. In contrast with the lifespan of RBCs from healthy donors (HD) or even individuals with sickle cell trait (SCT) who have been shown to have an RBC lifespan of approximately 107-115 days (2-4), the mean life span of RBCs in patients with SCD is approximately 10-32 days (2, 5-6). Certain molecular factors are thought to affect the severity of anemia in patients with SCD, likely reflected by different rates of hemolysis and therefore different hemoglobin levels at steady state. Several biochemical markers of hemolysis have a correlation to erythrocyte survival in patients with SCD, including a strong inverse correlation with absolute reticulocyte count (ARC) ( $r=-0.84$ ,  $p<0.0001$ ), percent of reticulocytes ( $r=-0.78$ ,  $p=0.002$ ),  $\alpha$  globin gene number ( $r=-0.15$ ,  $p=0.008$ ), and a positive correlation with percent fetal hemoglobin (HbF) ( $r=0.58$ ,  $p=0.038$ ) (2,4). The range of HbF content in fetal hemoglobin containing cells (F cells) appears to be important, with cells on the high end of the range surviving longer than those on the low end (7). Furthermore, the survival of non-F cells correlates inversely with the fraction of F cells, with shorter non-F cell RBC lifespan in patients with a high percentage of F cells independent of hydroxyurea therapy (7).

There are two methods to determine red cell survival; *in vivo* cohort methodology or *in vitro* population labeling. Cohort labeling involves labeling hemoglobin with oral glycine containing radioactive or stable isotopes ( $^{15}\text{N}$ -glycine) which becomes metabolically incorporated into hemoglobin-synthesizing normoblasts in the bone marrow (BM). The resulting labeled RBCs are similarly aged, and mature and are released from the BM at the same time. The quantification of RBC lifespan would therefore require a full time-course study of approximately 150 days (based on HD data and time to maximum  $^{15}\text{N}$ -glycine detection) and analysis by mass spectrometry. While this method allows study of single age cohort and does not require *ex vivo* manipulation, samples are not analyzed until the completion of the study and would therefore not be available live throughout the study.

In contrast to the cohort method, current population labels include biotin and  $^{51}\text{Cr}$ , which tag a representative population of circulating RBCs irrespective of RBC age. The ideal label has minimal RBC manipulation, stability throughout the life of the RBC, lack of RBC shortening due to labeling, and lack of toxicity to the individual receiving labeled RBCs. Biotinylated RBCs (BioRBCs) confer advantages over radiolabeled methods by upholding these ideals in addition to posing no radiation risks and providing a more acceptable method to study vulnerable populations such as women, fetuses, infants, and children. A further advantage of the population study method is the label (ie. biotin) can be easily tracked via flow cytometry, and the analysis can be complexed with additional characterization parameters such as intracellular staining for different hemoglobin moieties. The labeled population of cells is representative of what is found in circulation at the time of labeling and therefore the RBCs are of different ages. This type of study has allowed for measurement of phosphatidylserine exposure on RBCs as they age *in vivo* (8) and the quantification of lifespan of F cells versus non-F cells in SCD patients as previously described (7).

Additionally, a retrospective analysis of a population study data set suggests that a 28-day window may be sufficient for accurate quantification of MPL(4).

The only currently available cure for SCD is bone marrow transplantation (BMT), with gene therapy research active and underway. Stable, mixed donor-recipient chimerism after BMT is sufficient to reverse the sickle cell phenotype by virtue of improved donor red cell survival compared to the ineffective erythropoiesis of SCD (9). A previously developed mathematical model to test the hypothesis that the percentage of necessary donor myeloid chimerism is determined solely by the differences between donor and recipient RBC half-lives has been described (10). As stable mixed chimerism is intrinsically linked to the differences in RBC survival in healthy vs. the SCD genotype, understanding the variability and predictors of red cell survival among patients with SCD vs. individuals with SCT and healthy donors is critical for applied work in gene therapy research which seeks to generate sufficient corrected hemoglobin to overcome the red cell pathology of SCD.

Here we described a method to study the MPL of RBCs from patients with SCD, compared to patients who have successfully undergone curative BMT, individuals with SCT, and healthy donors without SCD, the latter two who serve as donors for patients with SCD who undergo BMT. Unlike biotinylation data from patients with SCD and healthy donors, the MPL of RBCs from participants with SCT has only previously been validated using the  $^{51}\text{Cr}$  population method (3). As individuals with SCT are valuable donors to patients with SCD undergoing HSCT, validation of the biotinylation method in this important population is critical. Understanding the differences in MPL of RBCs from these groups using a uniform method may ultimately guide gene therapy protocols to determine adequate hemoglobin content, ie. vector copy number (number of lentiviral vector copies carrying the therapeutic gene of interest in individual target cells, VCN) and/or the amount of corrective fetal or adult globin, required to overcome the SCD phenotype as it relates directly to red cell survival. Such application in the gene therapy patients will help target the percentage of transferred globin needed to reverse SCD based on a patient's engraftment, VCN or transferred globin editing, and red cell survival.

## 2.0 Objectives

- 2.1 Primary: To determine and compare red blood cell survival in patients with SCD, patients with SCD who have undergone hematopoietic stem cell transplantation, participants with SCT, and healthy donors, and validate the association of red cell survival with known markers of increased red cell survival including ARC, % HbF, and F cell percentage.
- 2.2 Exploratory: To create a mathematical model incorporating RBC survival and reticulocyte count to determine the necessary amount of normal hemoglobin, and therefore VCN or amount of edited/transferred globin, required for gene therapy protocols. This model can be validated by studying lifespan in patients after gene therapy treatment.

## 3.0 Scientific and Clinical Justification

The safety of biotinylating RBCs in SCD patients is known as is a shortened RBC survival. Known influencers of RBC survival such as ARC, %F, and F cells, and mixed chimerism after BMT is sufficient to reverse the sickle phenotype by virtue of improved donor red cell survival compared to the ineffective erythropoiesis of SCD. The percentage of transferred globin necessary to cure SCD through a gene therapy approach and the relationship among ARC, amount of HbA and/or HbF, and measured red cell survival is currently unknown. Furthermore, RBC survival in patients with SCD who have successfully undergone HSCT has never been performed, as has the biotin methodology for individuals with SCT who are a critically important donor source for patients undergoing BMT.

Collection and biotinylation of RBCs in this study will allow the measurement and study of red cell survival in patients with and without SCD. The study of RBC survival and its relation to known influencers of red cell survival including ARC, % HbF, and F cell percentage will allow for the creation of a mathematical model that will help determine necessary amount of normal hemoglobin required to reverse the SCD phenotype. Such determination has the potential to influence current and future gene therapy protocols. Future questions include the ability to measure RBC lifespan in gene therapy patients, and the relationship of transferred globin (VCN) and percent engraftment of gene modified cells to the patient's RBC survival. As has been previously described (10), the reticulocyte fraction is a good proxy for RBC lifetime, and therefore gene therapy may be most efficacious in patients in which RBC survival is lowest (with highest reticulocyte count) as they would require lower amounts of normal hemoglobin production (lower levels of gene correction) to sufficiently reverse the SCD phenotype.

The population method will be used here to study RBC lifespan due to the safety, potential for a substantially shorter study period, and the possibility of being able to complex the labeling of the RBCs with other markers of interest.

## **4.0 Subject Eligibility**

### **4.1 Inclusion criteria:**

- 4.1.1 Age 18 or greater with a confirmed diagnosis of homozygous SCD (HbSS, HbSC, HbSB0), sickle cell trait (HbAS), or healthy volunteer (HbA)
- 4.1.2 Normal renal function: creatinine <1.5 mg/dL
- 4.1.3 Negative direct antiglobulin test (DAT)
- 4.1.4 Ability to give informed consent to participate in the protocol

### **4.2 Exclusion criteria:**

- 4.2.1 Any uncontrolled chronic illness other than sickle cell disease
- 4.2.2 Active viral, bacterial, fungal, or parasitic infection
- 4.2.3 Consumption of biotin supplements or raw eggs within 30 days
- 4.2.4 Blood loss within the previous 8 weeks >540mL
- 4.2.5 Pregnancy
- 4.2.6 Pre-existing, naturally occurring antibodies against biotin

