## **5.0 Study Design and Methods**

### **5.1 Description of Study Population and Recruitment**

This is a pilot single site study and participants will be enrolled at the NIH Clinical Center. Recruitment will occur from a pool of normal volunteers, individuals with known SCT or SCD, and patients with SCD who have successfully undergone curative hematopoietic stem cell transplant. Volunteers will be recruited through the Clinical Center Volunteer Office.

The recruitment ceiling is an N=40 to account for screen failures. Accrual will be stopped once the numbers of active participants who have completed data collection have been reached:

- Normal Volunteers: N=3
- Individuals with SCT: N=6
- Individuals with SCD pre-transplantation: N=6
- Individuals with SCD post-transplantation: N=6-10

Accrual will be based solely upon protocol entry criteria and no selection will be based upon gender, race, or age (in those 18 years or greater in age). The study will be listed on the clinicaltrials.gov, Clinical Center research studies, and the National Heart, Lung and Blood Institute patient recruitment websites.

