**Table 2 Assessment Parameters**

Visit	Parameter	Additional History
Screening	CBC Reticulocyte count Hemoglobin electrophoresis Acute Care Panel Mineral Panel Hepatic Panel DAT ABO/Rh and antibody screen LDH Biotin antibody screen* Serum pregnancy test (females)  **HIV-1/HCV/HBV (NAT) Hepatitis B (surface antigen) Hepatitis B (core antibody) Hepatitis C (antibody)	Complete history including past medical history, transfusion history, bleeding history, and medications. A complete SCD history (where applicable) will include hydroxyurea use and dose, pain crisis frequency, ER and hospitalization utilization, and transfusion history.

	HTLV I and II (antibody) **HIV 1 and 2 (antibody) West Nile Virus T cruzi (antibody) Treponema pallidum (antibody) or equivalent (such as RPR) Urinalysis	
Week 1/Day -1 (Blood Collection)	CBC Reticulocyte count DAT Serum pregnancy test (females) α-Globin genotype  Infectious screening of whole blood per DTM (see 6.3)	Interim illness update (specifically for SCD patients, history of pain crisis, transfusion, ER visit, or recent hospitalization)
Week 1, Day 1 (Infusion Day)	For [name] Lab& bluebird bio  % survival biotinylated RBCs Hemoglobin content F cell percentage Delay time analysis HbF staining HbS single cell Western Blot Assay development	
Study Assessments (Time Zero – End of Study*)	Clinical Lab & DTM [name] & [name] Labs, bluebird bio  CBC Reticulocyte count Acute Care Panel Mineral Panel Hepatic Panel LDH DAT ABO/Rh and antibody screen Hemoglobin electrophoresis Biotin Antibody Detection*	% survival biotinylated RBCs Hemoglobin content F cell percentage Delay time analysis HbF staining HbS single cell Western Blot Assay development  Interim illness update as above

\*Biotin antibody detection will be done at initial screen, during the course of the study if bioRBC degradation is faster than predicted, and at 3 and 6 months post-infusion for all patients regardless of end of study date.

\*\*Gene Therapy patients may have other HIV testing, including HIV ½ Antibody/Ag Combo.

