## 7.0 Analysis of the Study

**7.1 Flow Cytometry Analysis:** Enumeration of BioRBCs will be performed by flow cytometry. Samples will be collected pre and post biotinylation prior to infusion (as per section 6.6), at 20 minutes post infusion (time zero), and as described in section 6.9 & Figure 1. To isolate the RBC fraction, 40 µL of whole blood aliquoted in triplicate will be mixed with 1 mL of wash buffer, centrifuged at 10,000 x g until the rpm value is reached, and supernatant will be discarded (repeat x1). The final washed RBC pellet will be resuspended in 80 µL of wash buffer, mixed with 20 µL of a 1:20 dilution (in PBS) of streptavidin-phycoerythrin (SA-PE; S-866; Molecular Probes, Eugene, OR), and incubated for 30 min at room temperature in the dark. The staining reaction is stopped by adding 3 mL of wash buffer, centrifuging at 1500 rpm for 5 minutes, and removing the aspirate. RBCs will then be suspended in 500 µL of wash buffer, and will be filtered through a 0.45 µm filter prior to flow cytometry (FACSCalibur, BD Biosciences, San Jose, CA). Percentages of BioRBCs will then be measured by flow cytometry.

**7.2 F-cell and S-cell measurement:** Simultaneously with the measurement of BioRBCs by flow cytometry (see section 7.1), samples will be analyzed with an additional color (3-color flow cytometry) for Biotin, HbF, and HbS. After incubation with SA-PE and two washes, the cells will be mixed with a 2 µL/mL solution of glutaraldehyde/PBS. Cells will be gently mixed and incubated at room temperature for 10 minutes. Cells will be centrifuged at 2500 rpm x 5 min, then incubated at room temperature with 1mL 0.1% Triton X solution for 10 minutes. After centrifugation at 2500 rpm x 5 minutes, cells will be stained for 30 minutes at room temperature with a fluorescein isothiocyanate (FITC)-conjugated monoclonal antibody to HbS and allophycocyanin (APC)-conjugated monoclonal antibody to HbF prior to analysis by flow

cytometry. The F per F cell can be calculated from the percent F cells, the percent HbF (determined by HPLC, see section 7.3), and the MCH.

7.3 **Hb Content:** BioRBCs will be isolated from post-infusion blood samples using streptavidin-coated magnetic beads or flow cytometry separation. The collected BioRBCs and the negative fraction will be analyzed by high performance liquid chromatography (HPLC) for hemoglobin content.

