7.6 Data and Statistical Analysis: This is an exploratory study designed to test methodology and assay development for the purposes of studying red cell survival in patients with SCD. RBC survival curves will be generated for each participant. Mean potential RBC life span (MPL) will be determined by plotting the percentage of remaining biotinylated RBCs in circulation against time after transfusion. Median RBC survival and mean RBC age will be calculated from these curves. Correlation of mean RBC survival with known markers of red cell survival will be performed using Pearson Correlation. The mean of each participant's clinical laboratory values during the study period will be used for correlation with RBC survival. Average MPL among the groups studied will be examined descriptively using means and standard deviations. The differences between groups will be used to examine the feasibility and guide the design of larger, definitive studies; in this pilot study, statistically significant differences are not generally anticipated. Similarly, information regarding hydroxyurea use,  $\alpha$  globin genotype, etc are likely to not be powered to see an effect.

7.7 Mathematical Model: We assume that in erythropoietic homeostasis, RBC lifetime is proportional to the inverse of the reticulocyte fraction such that RBC survival is lowest in patients with the highest reticulocyte counts. We will subsequently develop a mathematical model to predict the percentage of necessary hemoglobin to reverse SCD from reticulocyte count and RBC half-life.

7.8 **Off Study Criteria:** Patients reserve the right to come off study for any reason during the study period. Patients may be taken off-study by the PI if there is a health-related event during the course of the study that affects RBCs lifespan or production of RBCs including hemorrhage or need for transfusion. In the event of pregnancy after infusion of biotinylated RBCs, the patient will remain on study unless directed otherwise by the patient.

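### MPL is read from a percentage of labelled cells, which equals survival only at constant red cell mass, but no entry rule requires SCD participants to be at steady state and no red cell count correction is planned.

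*Combined protocol and SAP*

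**What the plan says.** **Measurement.** Section 7.1 ends with a percentage: "Percentages of BioRBCs will then be measured by flow cytometry". Section 7.6 obtains MPL by "plotting the percentage of remaining biotinylated RBCs in circulation against time after transfusion" and takes median survival and mean cell age from the same curves. It mentions no correction for red cell count, hematocrit or mass, and it does not name the MPL estimator. For the correlations it uses each participant's mean laboratory value over the study period.

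**Model.** Section 7.7 states its premise openly: "We assume that in erythropoietic homeostasis, RBC lifetime is proportional to the inverse of the reticulocyte fraction".

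**Entry.** Section 5.1 says "Accrual will be based solely upon protocol entry criteria". Sections 4.1 and 4.2 contain nothing on a recent crisis, transfusion or hydroxyurea change. Item 4.2.1 excludes "Any uncontrolled chronic illness other than sickle cell disease". The nearest safeguards are 4.2.2 (active infection) and 4.2.4 ("Blood loss within the previous 8 weeks >540mL").

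**Data collected.** Table 2 provides for an SCD history at screening that "will include hydroxyurea use and dose, pain crisis frequency". On the collection day it asks for "history of pain crisis, transfusion, ER visit, or recent hospitalization". No rule uses these items to time labelling or to shape the analysis. Table 2 also lists a complete blood count (CBC) and reticulocyte count among the follow-up assessments.

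**After entry.** Section 7.8 allows the investigator to remove a participant for an event during the study that affects red cell lifespan or production. This is discretionary and does not reach events before labelling.

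**The concern.** The labelled percentage is a ratio. Its numerator falls as labelled cells die. Its denominator is all circulating red cells. If red cell mass grows during follow-up, new unlabelled cells dilute the label and the curve falls faster than cells die. If mass shrinks, the curve falls too slowly. Mass is most likely to be moving in the SCD arm, and that arm has no entry condition on steady state.

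The same departure affects the 7.7 model twice. The lifespan input is distorted as described, and when mass is rising through extra production the reticulocyte fraction no longer reflects lifespan alone. The arm has six participants (section 5.1), so a few distorted curves would carry weight in its estimates and in the model.

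**Working it through.** **Inputs from the protocol.** SCD MPL about 32 days (Synopsis); SCD mean lifespan 10 to 32 days (section 1.0); a 28-day window may suffice for MPL (section 1.0); SCD pre-transplant N=6 (section 5.1). The plan has no figure of its own on this bias to reproduce.

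**Assumption.** Red cell mass changes by a fraction g over 28 days, with g from -20% to +30%. The documents give no such figure. Relative mass is m(t) = 1 + g·t/28, and the observed percentage relative to time zero is S(t)/m(t), where S is true survival of the label.

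**1. Median survival, linear curve.** Solving (1 - t/L)/(1 + g·t/28) = 0.5 gives t50 = 0.5/(1/L + g/56).

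| g | L=32 (true 16.0 days) | L=10 (true 5.0 days) |
|---|---|---|
| +10% | 15.1 (-5%) | 4.9 (-2%) |
| +20% | 14.4 (-10%) | 4.8 (-3%) |
| +30% | 13.7 (-15%) | 4.7 (-5%) |

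**2. Straight-line MPL.** A least-squares line through the same curve at days 0, 3.5, 7, 10.5, 14, 21 and 28 (L=32) meets zero at 31.2, 30.6 and 30.0 days: about -2.5%, -4% and -6%.

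**3. Exponential mean.** With S(t) = exp(-t/L), the apparent mean is close to 1/(1/L + ln(1+g)/28). For L=32 this gives 28.9, 26.5 and 24.6 days (-10%, -17%, -23%). For L=10 it gives 9.7, 9.4 and 9.1 days.

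**4. Falling mass.** At g = -10% and -20% with L=32, the exponential mean is 36.4 and 42.9 days, and median survival on the linear curve is 17.0 and 18.1 days. The sign reverses.

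**5. Reticulocyte side, linear model, L=32.** Production per unit of time-zero mass is P = 1/L + g/28. The fraction at time t is P/m(t), and its 28-day average is P·ln(1+g)/g. The implied lifetime is the inverse.
- g = 10%: P = 0.03482, average 0.03319, lifetime 30.1 days (-6%)
- g = 20%: P = 0.03839, average 0.03500, lifetime 28.6 days (-11%)
- g = 30%: P = 0.04196, average 0.03670, lifetime 27.2 days (-15%)

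At time zero alone the values are 28.7, 26.0 and 23.8 days (-10%, -19%, -26%), but 7.6 uses study-period means for its correlations. If loss is proportional to mass, the rate is that of step 3 and the error reaches -23%.

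**6. Does correction work?** Multiplying each percentage by m(t) returns 32.0 days in both the linear and the exponential case. It is not a complete repair. If mass was already rising at 20% per 28 days before labelling, the labelled cells are younger than at steady state, and the corrected curve gives an initial-slope MPL of about 35.6 days and a median of 16.8 against 16.0.

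**The case against.** The strongest reply is that this is a pilot with descriptive aims, that 7.7 is exploratory and declares its assumption, and that partial safeguards exist: 4.2.2, 4.2.4, 7.8, and reinfusion as an outpatient (section 6.2), which makes labelling during a hospitalised crisis unlikely. The size also depends on an assumed mass change, on an estimator that 7.6 leaves open and on the true lifespan. All of this stands. It limits the size of the concern, but none of it corrects the curve or covers an event before labelling.

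Three stronger readings are tempting and are not supported.

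- *That the bias always shortens survival, with both model inputs erring the same way.* Step 4 shows the reverse when mass falls. If mass rises because cells live longer, as might happen on hydroxyurea, production need not exceed baseline, so step 5 does not carry over.
- *That the study would confirm the inverse relation between reticulocytes and lifespan for the wrong reason.* Six participants with an identical true lifespan of 32 days, no noise, and mass changes from -10% to +30% do give r = -0.99. But the Synopsis describes SCD lifespan as much more variable. In simulated sets of six with true lifespan uniform on 10 to 32 days, mass change uniform on -10% to +30%, and lognormal reticulocyte noise (SD 0 to 0.4), mean r was -0.98 to -0.59 without mass change and -0.97 to -0.58 with it. At SD 0.2 it was -0.82 against -0.81.
- *That 4.2.1 deliberately admits participants in crisis.* It only declines to make SCD itself an exclusion under that item. The gap is the absence of any steady-state statement.

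**Conclusion.** The point holds as a moderate one. The plan reads survival from a percentage, relies on constant red cell mass without saying so in 7.6, and neither requires nor checks that condition in SCD participants.

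For a true MPL of 32 days and an assumed 10% to 30% rise in mass over 28 days, the error runs from about -2.5% to -6% (straight-line MPL) through -5% to -15% (median) to -10% to -23% (exponential mean). It is smaller at shorter lifespans and opposite in sign when mass falls. Lifetime implied by the study-average reticulocyte fraction is off by about -6% to -15% in the linear model, and by up to -23% under exponential loss.

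Even the extremes computed here, 24.6 and 42.9 days, stay far below 115, so the contrast between SCD and healthy donors is not in doubt. What is exposed are the individual SCD estimates and the inputs to 7.7.

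**What to change.** 1. In 7.6, prespecify beside the raw percentage curve a second curve: labelled percentage multiplied by the same-day red cell count, relative to time zero, using the CBCs already planned. Name the MPL estimator and report MPL from both curves.
2. Repeat the marker correlation and the 7.7 fit with the corrected MPL. As a sensitivity analysis, repeat them without participants flagged by the Table 2 history (crisis, transfusion, hospitalisation) or by a marked trend in red cell count, with the flag defined in advance. This should not replace the main fit, because dropping participants shrinks an arm of six.
3. State in section 4 or 6.3 that SCD blood collection for labelling is intended at steady state. The definition and time window are for the clinical team; the documents do not support a particular number of days.

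**Cost.** A little extra analysis and a few sentences of text, with no new samples. Some SCD collections may be deferred, depending on the definition chosen. Red cell count is a concentration, so the correction assumes constant blood volume, and it overshoots if mass was already rising before labelling. Both curves should therefore be shown.
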